4.2.2 Secondary Analyses

1. Treatment related AEs: Time to discontinuation of medication due to AEs will be compared by treatment arm using the Kaplan-Meier approach and log-rank test; Proportion of participants with Grade 3 or Grade 4 clinical AEs or laboratory abnormalities will be compared by treatment arm, using Fisher's exact tests.
2. Change in neurocognitive scores: See 4.2.1 Primary Analysis above.
3. Change in functional status: Pairwise comparisons will be performed among three treatment arms using the Wilcoxon rank-sum test.
4. Change in biomarkers: The Wilcoxon signed-rank test will be used to assess the changes from baseline to week 48 in specified biomarkers. Comparisons of changes in these biomarkers between any two treatment arms will be conducted through Wilcoxon rank-sum test.
5. Plasma HIV-1 RNA: For each treatment arm, the proportion of participants with ≥ 50 copies/mL and associated 95% CI will be provided in a table and plotted over time; Two-sided 95% CIs will also be provided for the difference between arms.
6. Changes in CD4+ cell counts: Average CD4+ counts and their associated 95% CIs will be provided and plotted over time for each treatment arm; changes in CD4+ counts from baseline to weeks 24, 48, and 96 will be compared pairwise among treatment arms through Wilcoxon rank-sum test.
7. Changes in CD8+ cell counts: Average CD8+ counts and their associated 95% CIs will be provided in a table and plotted over time for each treatment arm; changes in CD8+ counts from baseline to weeks 24, 48, and 96 will be compared pairwise among treatment arms through Wilcoxon rank-sum test.

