1.1 Purpose

This Primary Statistical Analysis Plan (SAP) describes the primary and secondary outcome measures and additional outcome measures of the A5324 study that will be included in the primary manuscript, and which address, at a minimum, the major primary and secondary objectives of the study. The Primary SAP outlines the general statistical approaches that will be used in the analysis of the study. It has been developed to facilitate discussion of the statistical analysis components among the study team, and to provide agreement between the study team and statisticians regarding the statistical analyses to be performed and presented in the Primary Analysis Report. It also describes the results for the primary and secondary outcome measures that will be posted on ClinicalTrials.gov.

Detailed outlines of tables, figures, and coding descriptions that will be included in the Primary Analysis Report are included in the Analysis Implementation Plan (AIP).

Analyses for the Primary Analysis Report will be finalized once the last participant has completed the week 96 study visit, all queries have been resolved, and the study database closure/data lock has been completed.

Outlines of analyses for other objectives and outcome measures not included in the Primary SAP will be provided in a separate SAP.

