2.1 Study Design

This is a phase IV randomized, double-blinded, placebo-controlled study to assess the efficacy of adding Maraviroc (MVC) and Dolutegravir (DTG) to the current antiretroviral therapy (ART) of HIV-infected individuals with undetectable (<50 copies/mL) plasma HIV-1 RNA, who have mild to moderate neurocognitive impairment, with a primary outcome of improvement in neurocognitive performance.

DURATION 96 weeks

SAMPLE SIZE 186 participants

POPULATION Participants will have HIV-associated neurocognitive disorder (HAND) as defined by the Frascati criteria, plasma HIV-1 RNA <50 copies/mL within 90 days prior to entry, and no more than one plasma HIV-1 RNA ≥ 50 and <200 copies/mL in the past 6 months prior to entry with a subsequent plasma HIV-1 RNA <50 copies/mL, and on stable ART for at least 6 months prior to entry with no plans to change treatment.

STRATIFICATION Participants will be randomized in a stratified manner. Stratification variables will be CD4+ nadir (≤ 100 vs. > 100 cells/mm³), and HAND severity (asymptomatic neurocognitive impairment [ANI] vs. mild neurocognitive disorder [MND] / HIV-associated dementia [HAD]).

REGIMEN At entry participants will be randomized to one of the following:
- Arm A: Add to their existing ART: placebo for MVC and placebo for DTG
- Arm B: Add to their existing ART: DTG and placebo for MVC
- Arm C: Add to their existing ART: MVC and DTG

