2.4 Overview of Sample Size Considerations

Based on previous studies, a standard deviation (SD) of 0.7 in the 48-week change in normalized neurocognitive test score is assumed. In the sample size calculation, the null hypothesis is that there is no difference in changes of neurocognitive functioning from baseline to week 48 across the treatment arms, while the alternative hypothesis is that the change of neurocognitive functioning is at least 0.5 higher for the (MVC and DTG) arm. A Bonferroni correction has been applied to account for multiple comparisons between treatments. One interim analysis of efficacy

is planned in the middle of the study and the adjusted sample sizes assume a 15% loss to follow-up. To achieve a power of 90%, we would expect a sample size of 62 participants per group for a total 186 participants on study. See Protocol section 9.4 for further details.

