3.2 Secondary Outcome Measures

1. Treatment related adverse events
 - Aligns with Secondary Objective 1
 - **Time to discontinuation of any study medication due to adverse events**
 - **Proportion of Grade 3 or Grade 4 clinical AEs**
 - **Proportion of Grade 3 or Grade 4 laboratory abnormalities**
 - **Summaries of all AEs where the site indicated some relationship to study treatment.**
2. Change from baseline of normalized composite neurocognitive test score at weeks 24, 72, and 96. Change from baseline of normalized component neurocognitive test scores at weeks 24, 48, 72, and 96 will also be examined.
 - Aligns with Secondary Objective 2
 - See primary outcome for details on composite neurocognitive test scores
 - Component neurocognitive test scores consist of domain scores

- Change from baseline in the domain deficit scores and GDS to weeks 24, 48, 72, 96
3. Change from baseline in functional status scores based on the IADLs form at weeks 24, 48, 72, and 96.
 - Aligns with Secondary Objective 3
 - **Functional change is defined as a change from baseline in IADL score. The IADL scoring is defined in Section 7.**
 4. Change from baseline of peripheral blood and CSF biomarkers at week 48.
 - Aligns with Secondary Objective 4
 - Potential list of biomarkers includes:
 - i. Blood: sCD14, MIP-1 β , TNFr-II, VCAM-1, NFL
 - ii. CSF: MIP-1 β , NFL, neopterin, IP-10
 5. Plasma HIV-1 RNA \geq 50 copies/mL at weeks 24, 48, and 96.
 - Aligns with Secondary Objective 6
 6. CD4+ T-cell counts and changes from baseline to weeks 24, 48, and 96.
 - Aligns with Secondary Objective 7
 7. CD8+ T-cell counts and changes from baseline to weeks 24, 48, and 96.
 - Aligns with Secondary Objective 7

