4.1 General Considerations

- The primary analysis and secondary analyses will use the ITT principle (i.e. all randomized participants will be included in the primary analyses).
- The primary analyses will use “as randomized” for group assignment.
- **The missing values for neurocognitive test scores will be imputed at the test level in the following manner:**
 - **When missing values can be attributed to neurologic impairment, the worst 1% score will be imputed for the missing values. Note: If the participant was unable to perform the test due to a disability related to HIV-associated neurological disease (e.g., unable to follow or understand directions, severe impairment in motor controls) this was indicated on the appropriate neuropsychological examination form.**
 - **If the reason for missingness is unknown and observations exist both before and after the missing value, these scores will be averaged and that averaged value will be imputed for the missing value.**
 - **If the reason for missingness is unknown and observations do not exist after the missing value, scores will be imputed by the last observation carried forward method.**
- **Missing data prevalence (of visits and of neurocognitive test scores) will be summarized.**
- **For the neurocognitive test scores, Winsorized estimates may be used for extreme outliers after observing the data.**
- All programs that create permanent study-specific derived datasets or that contribute to analyses of the primary or secondary objectives will be validated according to CBAR SOPs. Primary and key secondary objective results will be verified through independent double programming.
- **Visit and analysis window details:**
 - **Visits occurred at screening, entry, and weeks 2(±1), 4(±1), 12(±2), 24(±2), 48(-4,+8), 72(-4,+8), and 96(-4,+8).**
 - **Analysis windows will be formed around each study visit using the midpoints between adjacent visits as cutoffs and potentially including assessments collected outside the recommended visit windows described in the protocol.**

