4.2.3 Other Analyses

1. Changes in virologic measures: Wilcoxon rank-sum test will be used to compare Arm A and Arm B to assess the effect of DTG intensification on virologic changes.
2. **BDI Analyses: Change will be compared pairwise among the three treatment arms using the Wilcoxon rank-sum test. Percent of participants with BDI score >13 vs ≤ 13 will be compared by arm using the Chi-Square test.**

3. Correlation Analyses: Spearman correlations and scatterplots will be used to assess associations between:
 - a. Peripheral blood and CSF biomarkers and neuropsychological performance at weeks 0, 24, 48, 72, 96 (weeks 0 and 48 only for CSF biomarkers).
 - b. Changes in blood immunologic markers and changes in neurocognitive performance from baseline to week 48.
 - c. Changes in blood biomarkers from baseline to week 48.
 - d. **DTG and MVC PK and neuropsychological performance at weeks 24 and 48.**

5 Report Contents

Detailed descriptions of the content for each of the following sections are given in the AIP.

- CONSORT Diagram
- Accrual – summarize enrollment
- Baseline characteristics
 - Age
 - Sex
 - Race
 - IV drug use
 - Country
 - Education
 - Primary Language
 - HAND diagnosis
 - Nadir CD4 count
 - CD4 count
 - Log10 HIV-1 RNA
 - Neurocognitive test score
- Study status
- Treatment status
 - Premature study treatment discontinuation reasons
- Study conduct
 - Missed visits
- Safety Summary
- Analysis of primary outcome measures
 - Subgroup analyses
 - Sensitivity analyses
- Analysis of secondary outcome measures
- Analysis of other outcome measures

6 Appendix: Neuropsychological Norms For ACTG A5324

Domestic Sites

Trail Making A & B, Grooved Pegboard, Semantic and Letter Fluency

Norm source: Heaton RK, Miller SW, Taylor MJ, Grant I. (2004). Revised comprehensive norms for an expanded Halstead-Reitan battery: demographically adjusted neuropsychological norms for African American and Caucasian adults. Lutz, FL: American Psychological Assessment Resource, Inc.

- T scores were generated using the manual look-up tables.
- T scores were then converted to z-scores.
- Norms for African Americans were used for Hispanic and Native American participants.
- Trails B used a cut-off time of 240 seconds instead of the expected time out score of 300 seconds. Scores ≥ 240 are imputed to 300 for calculating the T score (unless a comment from the site provides an exact time).

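### SAP 4.2.2 item 1 gives no rule for non-AE exits in the Kaplan-Meier analysis of AE-caused drug stops; if they are censored, the curve overstates the share stopping for AEs

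*SAP*

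**What the plan says.** SAP 3.2 lists this endpoint first under secondary outcome 1: "Time to discontinuation of any study medication due to adverse events". The word *any* matters, because under SAP 2.1 every participant takes two blinded products (maraviroc or its placebo, and dolutegravir or its placebo).

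The analysis is in SAP 4.2.2, item 1: "Time to discontinuation of medication due to AEs will be compared by treatment arm using the Kaplan-Meier approach and log-rank test". No other estimator is named for it. The item gives no censoring rule and mentions neither cumulative incidence nor competing risks. The missing-data rules in SAP 4.1 cover neurocognitive test scores only. The general principle there is "The primary analysis and secondary analyses will use the ITT principle".

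Three other places bear on the point:
- SAP 2.1 sets the follow-up: "DURATION 96 weeks".
- SAP 2.4 expects people to leave: "the adjusted sample sizes assume a 15% loss to follow-up".
- SAP 5 lists, among the report contents, "Premature study treatment discontinuation reasons", so the reasons for stopping will be available.

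Further detail is placed elsewhere: "Detailed outlines of tables, figures, and coding descriptions that will be included in the Primary Analysis Report are included in the Analysis Implementation Plan". That plan is not among the documents.

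**The concern.** The event is cause-specific. Someone who has stopped all study drug for a non-AE reason, has died or has left the study cannot later be recorded as stopping because of an AE. Kaplan-Meier with those people censored treats them as if they could still have the event later, at the same rate as those who remain. Its complement then answers a hypothetical question: how many would stop for AEs if nothing else ever took people off drug? A tolerability report needs the share who did stop for AEs.

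Tolerability is the first secondary objective (SAP 2.3.2). If the curve is read as a failure rate, it will be too high in each arm, and by more in an arm with more non-AE exits. Two arms with the same true share of AE stops could show different curves.

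**Working it through.** **The plan's own figure.** No rate or precision is stated for this endpoint. The only design figure that can be reproduced is 62 per arm, which is used below for the standard error. The inputs from SAP 2.4 are SD 0.7, difference 0.5, power 90% and 15% loss. I assume two-sided alpha 0.05/3, because the section mentions Bonferroni but gives no alpha:

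n = 2 × [0.7 × (2.394 + 1.282) / 0.5]² = 52.96, and 52.96 / 0.85 = 62.3.

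This agrees with 62. The point below does not depend on it.

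**Assumed inputs.**
- True AE-stop share by week 96, c: 5%, 10%, 15%, 20%.
- Other exits by week 96: 15%, 27.75% and 35%. The middle value assumes that the 15% loss applies to week 48 and continues at that rate: 1 − 0.85² = 0.2775. Loss to follow-up is not the same quantity as non-AE drug stopping, so the range is only indicative.
- Constant hazards over the 96 weeks, with all non-AE exits censored in the Kaplan-Meier analysis.

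**Formulas.** Let λ2 = −ln(1 − other exits). Solve for λ1 in c = λ1/(λ1+λ2) × [1 − exp(−(λ1+λ2))]. Then 1-KM = 1 − exp(−λ1), and the per-arm standard error is √[c(1−c)/62].

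**Worked case: c = 10%, other exits 27.75%.** λ2 = −ln(0.7225) = 0.3250 and λ1 = 0.1241. Check: 0.1241/0.4491 × (1 − 0.6382) = 0.100. Then 1-KM = 1 − exp(−0.1241) = 11.67%, an excess of 1.67 points. The standard error is √(0.09/62) = 3.81 points, so the excess is 0.44 SE.

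**All cases (1-KM at week 96, %).**

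| Other exits | c = 5% | c = 10% | c = 15% | c = 20% | Excess in SE |
|---|---|---|---|---|---|
| 15% | 5.41 | 10.82 | 16.21 | 21.60 | 0.15 to 0.31 |
| 27.75% | 5.85 | 11.67 | 17.48 | 23.26 | 0.31 to 0.64 |
| 35% | 6.14 | 12.25 | 18.33 | 24.37 | 0.41 to 0.86 |

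The excess runs from 0.4 to 4.4 points.

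**Second parameterisation.** Here o is the share actually observed to leave for other reasons. With H = −ln(1−c−o), 1-KM = 1 − exp[−H·c/(c+o)]. For c = 10%, this gives 10.6%, 10.9% and 12.0% at o = 10%, 15% and 30%. A simulation with 62 per arm and 5000 runs agrees. At o = 15%, mean 1-KM is 10.9% and mean Aalen-Johansen 10.0%. At o = 30% they are 12.1% and 10.1%. The sampling SD of 1-KM was 4.1 and 4.6 points in these two cases, larger than the bias.

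**Arm contrast.** Take c = 10% in both arms, with o = 10% in one and 30% in the other. The first arm gives 1 − exp(−0.2231 × 0.5) = 10.6%, and the second 1 − exp(−0.5108 × 0.25) = 12.0%. The difference of 1.4 points is spurious.

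**Timing.** If all other exits come before any AE stop, 1-KM reaches c/(1−o): 11.8% for c = 10%, o = 15%, and 14.3% for c = 10%, o = 30%. The latter excess of 4.3 points is just over one SE (4.3/3.81 = 1.1). If AE stops all come first, there is no excess.

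**The case against.** A reader might infer that the SAP commits to an inflated tolerability rate. The documents do not go that far.

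- **Censoring is inferred.** SAP 4.2.2 is silent on it. If participants with non-AE stops stayed in the risk set to week 96 and follow-up were complete, 1-KM would equal the cumulative incidence. Under the stated ITT principle that reading is possible, though not usual. The Analysis Implementation Plan may settle it, as may the protocol's statistical section, which is not in the text available here. This objection stands, so the point is conditional.
- **No 1-KM percentage is promised.** Item 1 speaks of comparing arms, whereas items 5 to 7 of the same section name proportions or averages with 95% CIs and plots. The log-rank comparison is a valid test of cause-specific hazards if censoring is otherwise non-informative. It would be wrong to infer that the arm comparison itself is invalid. Even so, a Kaplan-Meier curve is the natural output of item 1 and will be read as a rate.
- **Not every non-AE stop removes the risk.** A participant who stops one product for a non-AE reason can still stop the other because of an AE. The competing event must therefore be complete discontinuation.
- **The reasons table covers part of this.** If every other exit is a competing event, nobody is censored before week 96, and Aalen-Johansen at week 96 is simply AE stops divided by participants randomised. That is close to a count in the planned table. The gain is mainly in the curve, the week 48 estimate, the intervals and a stated rule.
- **The remedy has its own risk.** Someone lost because of an unreported AE would count as never having had the event, so tolerability failure could be understated. This stands, and calls for a sensitivity analysis.

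**Conclusion.** The point holds in conditional form. The SAP names Kaplan-Meier as the only estimator for a cause-specific event and does not say what happens to participants who leave for other reasons. If they are censored, 1-KM cannot fall below the share stopping for AEs, and it exceeds that share whenever AE stops follow other exits.

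The size rests wholly on assumed rates. Under constant hazards the excess is below one per-arm standard error throughout the range examined; it passes that mark only with high non-AE exits concentrated early. A between-arm distortion needs unequal non-AE exits, which nothing in the documents predicts. The primary analysis and the sample size are unaffected. It is a minor improvement, worth making because the rule is missing and the correction costs almost nothing.

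**What to change.** In SAP 4.2.2 item 1:

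1. Replace the Kaplan-Meier curve with the Aalen-Johansen cumulative incidence of AE-caused discontinuation of any study medication, by arm, with 95% CIs at weeks 48 and 96.
2. Define the competing events as discontinuation of *all* study medication for non-AE reasons, and death. State that a non-AE stop of one product alone leaves the participant at risk.
3. Treat loss to follow-up or study exit as a competing event, and add a sensitivity analysis that censors it, because an unreported AE may be the cause.
4. Keep the log-rank test, labelled as a comparison of cause-specific hazards.

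The cost is a few lines of SAP text and a little more code. No new data are needed, since reasons for stopping are already to be reported under SAP 5. The reported AE-stop rates would be slightly lower than from a Kaplan-Meier curve that censors other exits.

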For rare instances or emergency cases, the *Pharmacy Guidelines and Instructions for DAIDS Clinical Trials Networks* permits shipment by mail or courier of study product from the site directly to participants. This method should only be used on a short-term basis and if permissible by the site's institution. If this method is to be implemented, each site's Pharmacist of Record (PoR) must develop appropriate procedures for the shipment or courier of study product to identified participants in accordance with these guidelines, and document chain of custody. Prior to implementation, the site PoR must coordinate with site clinic staff to determine the appropriateness of this method for applicable protocols and participants.

4. In section 6.1, Schedule of Evaluations, the visit window for weeks 36 to 96 has been changed as shown below:

Evaluation	Screening	Pre-Entry	Entry	Post-Entry Evaluations (Weeks)									Confirmation of VF	Premature Study/Treatment Discontinuation
				2	4	12	24	36	48	60	72	84		
Visit Windows				± 1 wk	± 2 wks			- 4 wks, + 8	12 wks					

5. In section 6.2.3, Post-Entry Evaluations, the following instructions have been added to the On-Treatment Evaluations subsection:

Alternate Completion of Post-Entry Evaluations

- **If the participant's visit is postponed within the extended visit window, the site should ensure that the participant has sufficient supply of the study products to last him or her to the point when he or she can come to the clinic.**
- **If the participant does not have enough supply of study products to allow the visit to be postponed, the site must attempt to contact the participant by phone or other method available.**
 - During the remote contact for visit week 72 or week 96, the site should conduct a safety follow-up (such as inquiring about signs and symptoms) to determine if any AEs or serious adverse events (SAEs) have occurred since the last visit and if the participant needs medical follow-up. Additionally, the site should complete the questionnaires and adherence assessment per section 6.3.9, section 6.3.10, and MOPS section 4. All other evaluations and stored samples that will be missing for the visits, and the reason why they are missing, must be documented in the participant's study file.
 - At all visits except week 96, the site should confirm if the participant is able to

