receive a new supply of study medications if it is shipped via mail or sent via courier (see section 5.1.2). If a participant is unable to pick up or receive study medications via shipment or courier, the site should consult the study core team ([contact]) for further guidance.

- If safety laboratory evaluations, and a pregnancy test for female participants of reproductive potential, cannot be performed, the continuation of study treatment is at the discretion of the Investigator of Record (IoR). The site should inform the study core team of the decision of the IoR.

6. In section 6.2.4, Discontinuation Evaluations, the following instructions have been added to the Premature Treatment Discontinuation Evaluations subsection:

Alternate Completion of Post-Entry Evaluations

- The visit can be postponed within the extended visit window if needed to safely conduct a face-to-face clinic visit. If the participant can safely be seen in the clinic, the site should perform all the evaluations for the visit per the SOE in section 6.1, Letter of Amendment (LOA) #1, and LOA #2.
- If the visit cannot be completed with a face-to-face visit despite the extended visit window, the site must attempt to contact the participant by phone or other method available. During the remote contact for visit week 72 or week 96, the site should conduct a safety follow-up (such as inquiring about signs and symptoms) to determine if any AEs or SAEs have occurred since the last visit and the participant needs medical follow-up. Additionally, the site should complete the questionnaires and adherence assessment per section 6.3.9, section 6.3.10, and MOPS section 4. All other evaluations and stored samples that will be missing for the visits, and the reason why they are missing, must be documented in the participant's study file.

7. In Appendix I, Sample Informed Consent (SIC), the following has been added as a new subsection, before the Optional Lumbar Puncture subsection, in the section WHAT DO I HAVE TO DO IF I AM IN THIS STUDY?:

COVID-19 Pandemic Considerations

During the ongoing COVID-19 pandemic, the following adjustments may be made to your study visits:

- If there is an outbreak of COVID-19 in your community and you are unable to come to the study clinic, your study doctor or staff member will try to contact you by phone or other remote method if you have a study visit due. During this contact:
 - You will be asked about your health since your last study visit or contact.

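### Grade 3/4 adverse events and laboratory abnormalities are compared as crude proportions over 96 weeks with no allowance for follow-up, which dilutes a between-arm difference when participants leave, or laboratory tests are missed, before a first event

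*SAP*

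**What the plan says.** SAP 4.2.2 item 1 gives two safety analyses. For stopping medication: "Time to discontinuation of medication due to AEs will be compared by treatment arm using the Kaplan-Meier approach and log-rank test". For severe events: "Proportion of participants with Grade 3 or Grade 4 clinical AEs or laboratory abnormalities will be compared by treatment arm, using Fisher's exact tests". The first allows for censoring; the second does not.

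On the population, SAP 4.1 states "The primary analysis and secondary analyses will use the ITT principle". Its explanatory parenthesis, "all randomized participants will be included in the primary analyses", spells out the denominator for the primary analyses only, and no separate safety denominator is given. The imputation rules in 4.1 concern neurocognitive test scores. For other missing data, the plan says only "Missing data prevalence (of visits and of neurocognitive test scores) will be summarized".

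SAP 2.1 sets a duration of 96 weeks. On attrition, SAP 2.4 says "the adjusted sample sizes assume a 15% loss to follow-up", with no figure by arm.

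The letter of amendment in the protocol file (items 5 and 6, changing protocol sections 6.2.3 and 6.2.4) allows remote contact when a clinic visit is not possible. At week 72 or 96 that contact includes a safety follow-up "to determine if any AEs or serious adverse events (SAEs) have occurred since the last visit", plus questionnaires and adherence. Beyond these, "All other evaluations and stored samples that will be missing for the visits, and the reason why they are missing, must be documented". Item 5 also foresees that safety laboratory tests may not be done while study treatment continues at the investigator's discretion.

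**The concern.** A crude proportion over all randomized participants treats each of them as observed for the full 96 weeks. Someone who leaves at week 10 without an event enters the numerator as zero and the denominator as one. For laboratory abnormalities the same happens when the sample was not taken, because an abnormality that is not measured cannot be counted.

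Safety and tolerability is Secondary Objective 1 (SAP 2.3.2). If one arm loses more participants, its observed Grade 3/4 proportion is pulled down further than the other's, and the comparison weakens when loss is greater in the arm with more events. The discontinuation analysis does not fill this gap, because a Grade 3/4 event, a laboratory one in particular, need not end study medication.

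**Working it through.** **1. The plan's own figure.** The only design figure is 62 per arm, for the primary outcome. With SD 0.7, difference 0.5, power 90% and two-sided alpha 0.05/3 (sidedness and divisor assumed from the three pairwise comparisons):

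n = 2 × [0.7 × (2.394 + 1.282)/0.5]² = 52.96; 52.96/0.85 = 62.3.

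This reproduces 62. It does not bear on safety except to fix n = 62 per arm below.

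**2. Inputs not in the documents.** Grade 3/4 risks and loss by arm are assumed, over a range. Event and loss times are taken as exponential and independent, with 96 weeks as the time unit and two-sided 0.05 per comparison.

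**3. What the crude proportion estimates.** Let h = −ln(1 − risk) and w = −ln(1 − loss). Then

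crude = h/(h + w) × [1 − (1 − risk)(1 − loss)].

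For true risks of 25% (h = 0.2877) and 40% (h = 0.5108):

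| Loss by arm | Lower-risk arm | Higher-risk arm | Apparent difference |
|---|---|---|---|
| none | 25.0% | 40.0% | 15.0 points |
| 15% / 15% | 0.2877/0.4502 × 0.3625 = 23.2% | 0.5108/0.6733 × 0.49 = 37.2% | 14.0 |
| 10% / 20% | 0.2877/0.3931 × 0.325 = 23.8% | 0.5108/0.7340 × 0.52 = 36.2% | 12.4 |
| 10% / 30% | 23.8% | 0.5108/0.8675 × 0.58 = 34.2% | 10.4 |

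The shrinkage is about 7% (1.0/15) at equal 15% loss and about 31% (4.6/15) at 10%/30%. With equal true risks of 20%, 10%/30% loss makes the higher-loss arm look 2.1 points safer.

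**4. Power at 62 per arm.** Fisher and chi-square power come from exact binomial enumeration on the crude proportions (4,000-trial simulations gave 35% to 36% for Fisher in the first row). Log-rank power comes from simulation.

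| True risks, loss | Fisher | Uncorrected chi-square | Log-rank |
|---|---|---|---|
| 25% vs 45%, 10%/30% | 36% | 43% | 62% |
| 25% vs 50%, 15%/15% | 73% | 79% | 81% |

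Chi-square uses the same crude proportions as Fisher, so the step from Fisher to chi-square measures Fisher's conservatism and the step from chi-square to log-rank measures ignored follow-up. In the first row these are about 7 and 19 points. In the second they are about 6 and 2.

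**5. Behaviour of the alternative.** With 20% vs 40% true risks and 10%/30% independent loss, the Kaplan-Meier difference averaged 0.200, against 0.151 for the crude difference. Log-rank type I error at 10%/30% loss was about 5%.

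**The case against.** A reader might infer that everyone who withdraws early, or who is seen only remotely, is scored as event-free. The documents do not support that. An event recorded before withdrawal counts, and the remote week 72 and 96 contacts must ask about adverse events. Only loss before a first event matters for clinical events, and only laboratory abnormalities can go unseen because a visit was remote.

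A reader might also infer that harm is hidden. Marked dilution needs a clear imbalance in loss, which the documents neither predict nor exclude. At the planned 15% in both arms the effect is slight, and most of the power gap there is Fisher's conservatism.

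Four further points have weight:

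- The all-randomized safety denominator is an inference from the intention-to-treat statement.
- The proportion is the named outcome in SAP 2.3.2 and 3.2, so dropping it would depart from the specified endpoint.
- Time to AE-related discontinuation, summaries of related events, and reports of missed visits and study status (SAP 3.2, 4.2.2 and 5) would make unequal loss visible. Detailed tables sit in the Analysis Implementation Plan, which is not available here.
- Loss caused by poor tolerability is informative censoring, and a log-rank test assumes that away.

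These limit the size of the point and argue for keeping the proportion. They do not remove it: the test is fixed in the SAP itself, it has no time element, and showing unequal loss in another table does not correct this comparison.

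**Conclusion.** The point holds in a limited form. The Grade 3/4 comparison ignores follow-up time over 96 weeks, although the same SAP item already uses a censoring method for a neighbouring outcome. The consequence is a difference that is diluted rather than removed: about 1 of 15 points at equal 15% loss, and about 4.6 of 15 at 10%/30%. In the 25% vs 45% scenario with 10%/30% loss, ignored follow-up costs about 19 of the 26 power points between Fisher and log-rank.

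All of this rests on assumed risks, assumed loss by arm, constant hazards and loss unrelated to event risk. The laboratory part stands apart from withdrawal, because tests may be missed while treatment continues; its size cannot be estimated from the documents. Fisher's test remains a valid comparison of the observed proportions, so this is an inexpensive improvement of low to moderate priority and not an error that invalidates the safety analysis.

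**What to change.** In SAP 4.2.2 item 1:

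- Add time to first Grade 3/4 event as the between-arm comparison, separately for clinical events and laboratory abnormalities: Kaplan-Meier week-96 risk with 95% CI and pairwise log-rank tests. Censor clinical events at the last adverse-event contact and laboratory events at the last safety laboratory sample.
- Keep reporting the proportion of participants with events, with its denominator stated. SAP 2.3.2 and 3.2 speak of the proportion of events, while 4.2.2 speaks of participants; reconcile the unit.
- Report follow-up time and the number of participants with a post-baseline safety laboratory test, by arm.

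The cost is SAP wording and routine programming, assuming event, contact and sample dates are already in the database. The downside is reliance on non-informative censoring, which may fail if participants leave because of poor tolerability. Censoring at the last sample also does not recover laboratory tests skipped mid-study, which is why the numbers tested should be shown.

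A competing-risk display for AE-related discontinuation is a separate, optional refinement.
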